#### 4.5.4 12-MONTH (+/- 30 DAYS) FOLLOW-UP VISIT

Trial subject follow-up clinic evaluation must occur 12 months post-procedure. The assessment will consist of:

- Vital signs
- Collection of BP (following the methodology for measurement as outlined in APPENDIX 3: METHODOLOGY FOR OFFICE-BASED BP MEASUREMENT)
- Physical exam
- Collection of concomitant medications
- Collection of AEs, if applicable

#### 4.5.5 18-MONTH (+/- 30 DAYS) PHONE CALL

Trial subject follow-up telephone contact evaluation must occur 18 months post-procedure. The assessment will consist of:

- Collection of concomitant medications
- Collection of AEs, if applicable

#### 4.5.6 24-MONTH (+/- 60 DAYS) FOLLOW-UP VISIT

Trial subject follow-up clinic evaluation must occur 24 months post-procedure. The assessment will consist of:

- Vital signs
- Collection of BP (following the methodology for measurement as outlined in APPENDIX 3: METHODOLOGY FOR OFFICE-BASED BP MEASUREMENT)
- Physical exam
- Collection of concomitant medications
- Collection of AEs, if applicable

#### 4.5.7 36-MONTH (+/- 60 DAYS) FOLLOW-UP VISIT

Trial subject follow-up clinic evaluation must occur 36 months post-procedure. The assessment will consist of:

- Vital signs
- Collection of BP (following the methodology for measurement as outlined in APPENDIX 3: METHODOLOGY FOR OFFICE-BASED BP MEASUREMENT)
- Physical exam
- Collection of concomitant medications
- Collection of AEs, if applicable

#### 4.6 CONCOMITANT MEDICATIONS

All medications (prescription, herbal, and over-the-counter) taken from the time of informed consent through 3 years must be recorded in the subject's source records and transcribed into the concomitant medication section of the eCRF.

Subjects are required to receive dual anti-platelet therapy pre-procedure and for a minimum of 3 months post-procedure. The required medications for this study are listed below.

**Table 2: Concomitant Medications**

Timing	Medication	Procedure
Prior to Procedure	IV Heparin or low molecular weight heparin or bivalirudin	Per routine hospital practice
	Acetylsalicylic acid (ASA)	ASA 325mg loading dose should be given the day of index procedure and prior to placement of the iCAST™ RX Stent System.
	Thienopyridine	The following loading dose of one of the below thienopyridines should be given the day of index procedure and prior to placement of the iCAST™ RX Stent System. Clopidogrel: $\geq 300\text{mg}$ Prasugrel: $\geq 60\text{mg}$ Ticlopidine: $\geq 500\text{mg}$
During Procedure	IV Heparin or low molecular weight heparin or bivalirudin	Per routine hospital practice
Post Procedure	Acetylsalicylic acid (ASA)	At least 75-325mg per day for a minimum of 3 months
	Thienopyridine	The following maintenance dose of one of the below thienopyridines should be given for a minimum of 3 months or longer based on local guidelines, except when it is medically necessary to take subjects off therapy. Clopidogrel: $\geq 75\text{mg}$ Prasugrel: $\geq 10\text{mg}$ Ticlopidine: $\geq 250\text{mg}$ (twice per day)

## 5.0 STATISTICAL CONSIDERATIONS AND ANALYSIS PLAN

### 5.1 ASSUMPTION OF PRIMARY ENDPOINT RATE

The endpoints will be tested in a sequential manner:

1) Functional Endpoint

Assessment of primary patency rate at 9-months, defined as continuous patency without the occurrence of a total occlusion of the original lesion, without a re-intervention to treat a partial or total occlusion of the stented segment, or bypass of the stented segment due to clinically-driven restenosis or occlusion.

Followed by:

2) Clinical Endpoint

Improvement in systolic blood pressure (SBP) at 9-months as compared to baseline systolic blood pressure.

If the null hypothesis for the functional goal is rejected at the 0.025 level of significance, the null hypothesis for the clinical goal will be tested at the 0.025 level. If rejected, success will be declared for both Performance Goals. Otherwise, if only the first (primary patency) null hypothesis can be rejected, success will be declared only for that Performance Goal. This sequential approach controls the overall significance level at 0.025. Of note, no success can be declared if the null hypothesis for the primary patency goal was not rejected, regardless of the outcome for the other Performance Goal.

For the primary patency endpoint, the proportion of subjects experiencing this outcome will be compared to the predefined Performance Goal of 0.70. Formally, the hypothesis to be tested is:

$H_0$ : The incidence  $p_{PP}$  of primary patency at 9-months is less than or equal to 0.70.

$H_0$ :  $p_{PP} \leq 0.70$

$H_A$ : The incidence  $p_{PP}$  of primary patency at 9-months is greater than 0.70.

$H_A$ :  $p_{PP} > 0.70$

The derivation of the Performance Goal is described in Section 5.2.1 Derivation of the Performance Goal for Patency.

For the SBP endpoint, the change between SBP from baseline to 9-month follow-up will be compared to a predefined Performance Goal of 10mmHg. Formally, the hypothesis to be tested is:

$H_0$ : The mean difference between SBP at 9-months and baseline,  $\mu_{\Delta\text{SBP}}$ , is less than or equal to 10mmHg.

$$H_0: \mu_{\Delta\text{SBP}} \leq 10\text{mmHg}$$

$H_A$ : The mean difference between SBP at 9-months and baseline,  $\mu_{\Delta\text{SBP}}$ , is greater than 10mmHg.

$$H_A: \mu_{\Delta\text{SBP}} > 10\text{mmHg}$$

Both primary endpoints will be tested in one-sided fashion against a significance level of 0.025; the primary patency endpoint will be tested using exact binomial methods and the SBP endpoint will be tested using a paired t-test.

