## 2.0 TRIAL OBJECTIVES

### 2.1 RATIONALE

The primary goal of revascularization therapy is the re-establishment and maintenance of adequate blood flow within the renal artery to perfuse the kidney. ARTISAN will investigate the re-establishment of adequate blood flow and normalized pressure in the renal artery and its effect on blood pressure in patients with resistant hypertension. In this single-arm trial, primary endpoints have been determined to show the safety, effectiveness, and clinical outcomes of the iCAST™ RX Stent System. Safety and effectiveness will be evaluated based on the primary patency rate at 9-months on a per lesion basis evaluated against a performance goal of published studies with bare-metal stents. The primary clinical endpoint will assess the improvement in SBP at 9-months as compared to baseline SBP.

The primary functional endpoint of primary patency has been established since the clinical care of the physician is considered a more objective measurement of stent performance than the restenosis measurement of DUS alone. In standard practice, a DUS is used to determine patency of a stent. If a DUS is negative and the patient is asymptomatic, no intervention is typically conducted by a physician. If a patient is symptomatic or a DUS is positive, a confirmatory angiogram is typically performed to assess the patency of the vessel.

To properly match the functional outcomes with historical data, the endpoint will be calculated on a per lesion basis. This reflects the current standard of care of treating patients with single

vessel renal artery lesions and those patients with bilateral renal artery stenosis. Analysis of past studies has demonstrated that the number of lesions treated per patient has increased with time. A recent renal trial reported 1.2 lesions per patient were treated. To calculate on a per patient level for this endpoint would bias the results and overestimate the failure rate compared to a per lesion analysis, as more lesions would be at risk for restenosis but would not be accounted for in a per patient analysis.

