### **3.2 INCLUSION CRITERIA**

Subjects must meet ALL of the inclusion criteria to be considered for the trial:

General Inclusion Criteria:

1. Age  $\geq 18$  at the time of informed consent.
2. Subject or subject's legal representative have been informed of the nature of the trial, agrees to participate and can comply with study procedures and follow-up, and has signed an IRB/EC approved ICF.
3. Subjects that have bilateral kidneys or a solitary functioning kidney with Renal Artery Stenosis in at least one kidney and an average SBP  $\geq 155\text{mmHg}$ .
4. Subject has a history of maximum tolerable dose of  $\geq 3$  anti-hypertensive medications of different classes, one of which must be a diuretic (for at least two weeks prior to Medical Documentation Screening period).
  - a. A documented history for a minimum of 3 months showing reasonable and aggressive efforts to manage hypertension prior to consent. This must include the use of a broad variety of medications that have been used and failed or not tolerated.
5. Subject must have documented clinical evidence to support likelihood of angiographic findings  $> 80\%$  whether it is DUS, CTa, MRa or other medical evidence..
6. NYHA class I, II, or III the time of trial enrollment.

NOTE: When a subject has bilateral Renal Artery Stenosis both of which require stenting, it is recommended to treat both kidneys with an iCAST™ RX Stent System during the index procedure. In the event that a subject needs a renal stenting procedure staged for renal protection, it is important that the Investigator treats the second renal artery with an iCAST™ RX Stent System after 30 days of the index procedure. If subjects with bilateral stenosis have only one lesion that meets protocol inclusion criteria that lesion should be treated per protocol. The recommendation is to NOT treat the second non-qualifying lesion, however if the operator feels strongly it is indicated, then they should treat per standard of care after 30-days post index procedure in order to comply with exclusion criteria #10.

Subjects with flash pulmonary edema are allowed into the trial should they meet all other Inclusion and Exclusion criteria.

Angiographic Anatomic Inclusion Criteria:

1. Angiographic diameter renal artery stenosis  $\geq 80\%$  involving unilateral or bilateral renal arteries.
  - a. The degree of percent diameter stenosis for all lesions intended to be treated, must be confirmed via one of the following methods:

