## 5.2 SAMPLE SIZE

For a one-sided alpha of 0.025 and desired power of 87%, sample size for the primary patency endpoint is established by assuming a hypothesized primary patency incidence of 0.82, which gives 125 evaluable subjects therefore, accounting for 10% attrition, 138 subjects are needed for this endpoint. At the proposed evaluable sample size of 125, no more than 27 subjects (22%) can fail primary patency in order to meet the endpoint hypothesis.

For the endpoint of reduction in SBP, we assume an average reduction of 13.7mmHg. Under a hypothesized standard deviation of 12mmHg for a difference in SBP there will be 92% power to meet the Performance Goal. This standard deviation is conservatively approximated based on the expected range of SBP at baseline of 155mmHg to 180mmHg divided by 3 and assuming a similar standard deviation at the 9-month follow up. A mean difference in SBP at 9-months of 12mmHg will be required in order to reject the null hypothesis at a one-sided alpha of 0.025 at the proposed sample size.

The primary endpoints of primary patency and reduction in SBP are powered at 87% and 92%, respectively, in order to maintain the overall trial power at 80% to meet both endpoints.

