8.8 Unit of Analysis

For the primary functional endpoint of primary patency rate the unit of analysis is the atherosclerotic lesion(s). The rationale for analyzing the primary endpoint following a per lesion approach, is to avoid overestimation of the failure rate, as more lesions would be at risk for restenosis but would not be accounted for in a per subject analysis.

Since blood pressure is measured on the subject level, the primary clinical endpoint of change SBP will be evaluated at the subject level.

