9.9.1. Primary Patency Analysis

The primary endpoint will be the cumulative incidence of primary patency at 9-months of study computed as the number of subjects with primary patency at 9-months divided by the number of subjects in the ITT population. An exact binomial one-sided 95% confidence interval will be constructed and the upper limit compared to the Performance Goal equal to 70%. A p-value for the one-sided exact test of the difference between the observed rate and the Performance Goal will be presented. The primary analysis will be analyzed with observed data only.

A planned subgroup analysis of the primary functional endpoint will be performed (details are provided in section 9.9.4

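### The patency test and limit treat lesions as independent although bilateral subjects contribute two, so the interval and p-value are too precise if outcomes within a subject are positively correlated

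*Protocol*

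**What the plan says.** **Unit.** SAP 8.8 is explicit ("For the primary functional endpoint of primary patency rate the unit of analysis is the atherosclerotic lesion(s"). SAP 7.6.1 divides patent lesions by subject-lesions, SAP 5.7 words the hypothesis in subject-lesions (arteries), and Protocol 2.1 also calls for a per-lesion calculation.

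**Two lesions per subject.** Where both renal arteries need stenting, Protocol 3.2 says "it is recommended to treat both kidneys with an iCAST™ RX Stent System during the index procedure". On frequency, Protocol 2.1 offers one outside figure: "A recent renal trial reported 1.2 lesions per patient were treated".

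**Test and limit.** Protocol 5.1: "the primary patency endpoint will be tested using exact binomial methods", and "Both primary endpoints will be tested in one-sided fashion against a significance level of 0.025". The patency proportion "will be compared to the predefined Performance Goal of 0.70". SAP 9.9.1: "An exact binomial one-sided 95% confidence interval will be" constructed and compared with 70%, with a one-sided exact p-value. SAP 9.9 still calls p-values below 0.025 significant.

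**Allowance for pairing.** There is none. The random-effects model in Protocol 5.3.6.4 is for sites and regions, SAP 8.6 drops pooling of centers, and SAP 8.2 plans no covariate adjustment. The reason given for the per-lesion unit (Protocol 2.1, SAP 8.8) is that a per-subject count would overstate failure; correlation is not mentioned.

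**Conflicting wording.** Protocol 5.1 and 5.2 speak of subjects, and SAP 9.9.1 itself divides subjects by subjects.

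**Status.** Enrollment stopped at 68 subjects (SAP 6.1). SAP 2, 6.2 and 8.7 make inference descriptive, without type I error control.

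**The concern.** The guarantee in the word exact depends on every unit being an independent trial with the same success probability. Two stents in one person share the patient's disease, renal function and antiplatelet adherence, and usually the operator and procedure. Positive correlation is therefore the natural expectation. If it is present, the lesions carry less information than their number suggests: the binomial standard error is too small, the limits lie too close to the estimate, and the p-value against 70% is too small.

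Patency is also the gatekeeper in Protocol 5.1, where no success can be declared unless it is met. In the trial as now analyzed, what is at stake is mainly the width of the reported interval and the size of the p-value.

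**Working it through.** **1. The plan's own figure.** The inputs are a null rate of 0.70, "assuming a hypothesized primary patency incidence of 0.82", one-sided 0.025, and 125 evaluable units with at most 27 failures (Protocol 5.2). For independent units:
- P(X ≥ 98 | 125, 0.70) = 0.0230
- P(X ≥ 98 | 125, 0.82) = 0.876
- With 28 failures allowed the error would be 0.0368, so 27 is the correct cut-off.

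The stated 87% power and 27 failures are reproduced for 125 independent units.

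**2. Model for pairs.** A subject contributes one or two lesions. Several lesions under one stent count as one (SAP 7.6.1), and arteries needing more than one stent are excluded (Protocol 3.3). With p = 0.70 and within-subject correlation ρ, a bilateral subject has:
- both patent: p² + ρp(1−p) = 0.49 + 0.21ρ
- one patent: 2p(1−p)(1−ρ) = 0.42(1−ρ)
- none patent: (1−p)² + ρp(1−p) = 0.09 + 0.21ρ

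The exact distribution of the lesion count is the convolution of the unilateral and bilateral subjects. The error is read at the pass mark that the ordinary exact binomial would set.

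**3. Assumptions.** A mean of 1.2 lesions per subject means about 20% are bilateral: 0.2 × 68 = 13.6, taken as 14, giving 54 + 28 = 82 lesions. All 68 subjects are taken as evaluable. For the planned size, 125 subjects with 25 bilateral give 150 lesions. The documents give no ρ, so a range is shown.

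**4. True one-sided error at 70% patency (nominal 0.025).**

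| Lesions (bilateral / subjects) | Pass mark | ρ = 0 | 0.3 | 0.5 | 0.8 |
|---|---|---|---|---|---|
| 82 (14 / 68) | 66 | 0.0223 | 0.0278 | 0.0316 | 0.0376 |
| 150 (25 / 125) | 117 | 0.0181 | 0.0228 | 0.0262 | 0.0314 |

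The 0.025 level is crossed at ρ of about 0.15 for 82 lesions and about 0.43 for 150.

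**5. Sensitivity to the number of bilateral subjects.** For 10 to 27 bilateral subjects of 68 at ρ = 0.8, the error runs from 0.024 (13 bilateral, 81 lesions, pass mark 66) to 0.048 (26 bilateral, 94 lesions, pass mark 75). The path is not smooth. The pass mark is a whole number, so the exact test's unused error sometimes absorbs the whole excess. Moving from 13 to 14 bilateral subjects takes the error from 0.0244 to 0.0376.

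**6. Standard error.** With m the number of lesions per subject, the design effect is 1 + (Σm²/Σm − 1)ρ. For 54 single lesions and 14 pairs, Σm² = 54 + 56 = 110 and Σm = 82, so it is 1 + 0.341ρ. This gives 1.10, 1.17 and 1.27 for ρ = 0.3, 0.5 and 0.8. The square roots are 1.05, 1.08 and 1.13, so the correct standard error is about 5%, 8% and 13% larger.

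**7. What this does to a limit.** The exact lower limit is the α quantile of Beta(x, n−x+1). At 66/82 patent the lower 97.5% limit is 0.703. With n and x divided by the design effect it is 0.697, 0.693 and 0.687, now below 0.70.

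The SAP's interval is one-sided 95%. On the lower side its nominal 0.05 error becomes 0.040, 0.053 and 0.061 for ρ = 0, 0.5 and 0.8 (82 lesions, pass mark 65).

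**The case against.** **The SAP has withdrawn error control.** True: SAP 2, 6.2 and 8.7 make inference descriptive. A reader might still infer that the trial risks a false confirmatory claim of patency above 70%; the documents do not support that. But SAP 9.9 and 9.9.1 keep the 0.025 threshold, the p-value and the comparison with 70%, and descriptive status does not correct an interval that is too narrow.

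**The excess may be nil.** Also true. A reader might infer that the error always exceeds 0.025 once pairs are correlated. It does not: at 81 lesions it is 0.0244 even at ρ = 0.8. SAP 9.9.1 also uses observed data only. With 61 evaluable subjects, 12 of them bilateral (73 lesions), the error is 0.0194 at ρ = 0.5 and 0.0237 at 0.8. With 62 evaluable and 12 bilateral (74 lesions) it is 0.0308 at 0.5. Only the word can is justified.

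**SAP 9.9.1 counts subjects.** Followed literally, it has no clustering. However, SAP 5.7, 7.6.1 and 8.8 all say lesion, and 8.8 argues against a per-subject count. The unit must therefore be settled first.

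**The limit may not favor the device.** Protocol 5.3.5.1 and SAP 9.9.1 compare the upper limit with 70%, and an upper limit that is too narrow is too low. The statement that the comparison is too lenient applies to a lower limit, the side that bears on exceeding 70%. The mismatch of level and side is a separate matter.

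**The correlation is assumed.** It is, and 0.8 is the high end of the range shown. Protocol 3.2 also lets the second artery be treated after 30 days, so a shared procedure is not universal. The patient is still shared.

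**Conclusion.** The method for the error bars is wrong as written: a per-lesion analysis with paired lesions is given a test and limit that assume independence. Under positive within-subject correlation the standard error is understated. The correct one is about 5% to 13% larger for correlations of 0.3 to 0.8 with 14 bilateral subjects of 68.

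The one-sided error may rise from 0.022 to between 0.028 and 0.038 at 82 lesions, and from 0.018 to between 0.023 and 0.031 at 150. Whether it passes 0.025 depends on the exact number of lesions.

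The result rests on three assumptions that the documents do not settle: the sign and size of the correlation, a bilateral share taken from another trial's 1.2 lesions per patient, and full evaluability. The effect is modest. With inference now descriptive, it is chiefly an interval and a p-value that look more precise than they are. It is worth correcting but does not undermine the trial.

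**What to change.** In SAP 9.9.1:

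1. Replace the subject-over-subject calculation with the lesion-over-subject-lesion calculation of SAP 7.6.1 and 8.8, or state openly that the unit has changed.
2. If the lesion stays the unit, base the p-value and the limit compared with 70% on a subject-clustered method. One option is an intercept-only GEE with subject as the cluster and a small-sample robust variance. Another is the exact interval on the effective sample size (lesions divided by the design effect), shown over a stated range of correlations, because about 14 pairs estimate the correlation poorly. Neither restores an exact guarantee, and the text should say so.
3. Report the per-subject rate (all treated lesions patent) with its exact interval as a supporting figure, and give the number of bilateral subjects.

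The cost is a short SAP edit and a few lines of code, with no new data. The interval becomes modestly wider, by about 5% to 13% for correlations of 0.3 to 0.8.

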## 5.2 SAMPLE SIZE

For a one-sided alpha of 0.025 and desired power of 87%, sample size for the primary patency endpoint is established by assuming a hypothesized primary patency incidence of 0.82, which gives 125 evaluable subjects therefore, accounting for 10% attrition, 138 subjects are needed for this endpoint. At the proposed evaluable sample size of 125, no more than 27 subjects (22%) can fail primary patency in order to meet the endpoint hypothesis.

For the endpoint of reduction in SBP, we assume an average reduction of 13.7mmHg. Under a hypothesized standard deviation of 12mmHg for a difference in SBP there will be 92% power to meet the Performance Goal. This standard deviation is conservatively approximated based on the expected range of SBP at baseline of 155mmHg to 180mmHg divided by 3 and assuming a similar standard deviation at the 9-month follow up. A mean difference in SBP at 9-months of 12mmHg will be required in order to reject the null hypothesis at a one-sided alpha of 0.025 at the proposed sample size.

The primary endpoints of primary patency and reduction in SBP are powered at 87% and 92%, respectively, in order to maintain the overall trial power at 80% to meet both endpoints.

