STATISTICAL METHODS	The sample size has been chosen to provide an adequate number of subjects to confirm the safety and efficacy of the iCAST™ RX Stent System. The co-primary endpoints of primary patency and reduction in SBP are powered at 87% and 92%, respectively, in order to maintain the overall trial power at 80% to meet both endpoints with a sample size of up to 138 subjects.
CO-PRINCIPAL INVESTIGATORS	
CONTRACT RESEARCH ORGANIZATION (MONITORING, DATA MANAGEMENT, DSMB, AND CEC)	
VASCULAR ULTRASOUND CORE LABORATORY	

ANGIOGRAPHIC CORE LABORATORY	[REDACTED]
MEDICAL MONITOR AND SAFETY	[REDACTED]
ELECTRONIC DATA CAPTURE	[REDACTED]
SPONSOR	Atrium Medical Corporation [name] [contact] [contact]

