**Figure 1: Medical Documentation Screening Period Flow Diagram**

### **3.5 SUBJECT ENROLLMENT**

Up to 138 subjects will be enrolled in this clinical trial. Eligible subjects will be enrolled consecutively at each investigational site. A patient is deemed enrolled into the trial once all inclusion criteria have been met and reviewed by an independent medical monitor, no exclusion criteria exist, the operator determines the target lesion is  $\geq 80\%$  diameter stenosis or FFR  $< 0.8$  and the trial device enters the subject. The screening log will then be completed to document the enrollment, subject number, or reason for non-enrollment of subjects screened but not enrolled in the ARTISAN trial.

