5.5 Determination of Sample Size

For a one-sided alpha of 0.025 and desired power of 87%, sample size for the primary patency endpoint is established by assuming a hypothesized primary patency incidence of 0.82, which

Amendment #1: 15Jul13

gives 125 evaluable subjects therefore, accounting for 10% attrition, 138 subjects are needed for this endpoint. At the proposed evaluable sample size of 125, no more than 27 subjects (22%) can fail primary patency in order to meet the endpoint hypothesis.

For the endpoint of reduction in SBP, we assume an average reduction of 13.7mmHg. Under a hypothesized standard deviation of 12mmHg for a difference in SBP there will be 92% power to meet the Performance Goal. This standard deviation is conservatively approximated based on the expected range of SBP at baseline of 155mmHg to 180mmHg divided by 3 and assuming a similar standard deviation at the 9-month follow up. A mean difference in SBP at 9-months of 12mmHg will be required in order to reject the null hypothesis at a one-sided alpha of 0.025 at the proposed sample size.

The primary endpoints of primary patency and reduction in SBP are powered at 87% and 92%, respectively, in order to maintain the overall trial power at 80% to meet both endpoints.

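### The attrition allowance is one subject short: 125 evaluable after 10% loss needs 139 enrolled, not 138, so the stated pass mark and power do not quite carry over to the stated enrolment

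*Protocol*

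**What the plan says.** Protocol 5.2 sets a one-sided alpha of 0.025 and a target patency power of 87%, "assuming a hypothesized primary patency incidence of 0.82", "which gives 125 evaluable subjects therefore, accounting for 10% attrition, 138 subjects are needed for this endpoint". It adds that, at 125 evaluable, at most 27 subjects may fail. SAP 5.5 repeats the step: "accounting for 10% attrition, 138 subjects are needed for" this endpoint.

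Protocol 5.1 fixes the test and the comparator: "the primary patency endpoint will be tested using exact binomial methods", and the proportion "will be compared to the predefined Performance Goal of 0.70".

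For systolic blood pressure, Protocol 5.2 assumes a mean reduction of 13.7 mmHg against a goal of 10 mmHg with SD 12 mmHg, for 92% power. The Protocol Summary describes the two endpoints as "powered at 87% and 92%, respectively, in order to maintain the overall trial power at 80" per cent, and attaches these powers to a sample of up to 138 subjects, not to 125 evaluable. Protocol 3.5 makes 138 a ceiling: "Up to 138 subjects will be enrolled in this clinical trial".

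**The concern.** The stated enrolment and the stated evaluable number do not correspond. An allowance for 10% loss divides the evaluable number by 0.90. The stated 138 looks instead like 125 multiplied by 1.10 (137.5, rounded up), which adds 10% of the smaller number and falls one subject short.

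One subject would normally be too small to mention. Here the test is exact, and 125 is the smallest sample at which 27 failures still pass. One fewer evaluable subject moves the pass mark, and the power moves with it. Patency is also the gatekeeper: under Protocol 5.1 no success can be declared if it fails. A reader who takes 138 enrolled and 10% attrition at face value would therefore carry over a pass mark and two power figures that do not belong to the resulting number.

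**Working it through.** **Inputs.** From Protocol 5.1 and 5.2: null rate 0.70; assumed rate 0.82; one-sided alpha 0.025; exact binomial test; blood-pressure goal 10 mmHg, assumed reduction 13.7 mmHg, SD 12 mmHg; 10% attrition. As in the plan, the unit is the subject.

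**Formulas.**
- Pass mark: the smallest r with P(X ≥ r | n, 0.70) ≤ 0.025. Failures allowed = n − r.
- Patency power: P(X ≥ r | n, 0.82).
- Blood-pressure power: one-sample t-test, noncentral t with n − 1 degrees of freedom and noncentrality (13.7 − 10)/12 × √n.
- Joint power: the product of the two. This treats the endpoints as independent, as the plan's own figure does (0.87 × 0.92 = 0.80).

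**Step 1: the plan's own figures at 125.** r = 98, so 27 failures are allowed; attained alpha 0.0230; patency power 87.6%; blood-pressure power 92.8%; joint power 0.876 × 0.928 = 81.3%. The stated 27, 87%, 92% and 80% are all supported.

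**Step 2: the attrition step.**
- 138 × 0.90 = 124.2, so 124 evaluable.
- 125 / 0.90 = 138.9, so 139 enrolled; 139 × 0.90 = 125.1.
- 125 × 1.10 = 137.5, which rounds up to the stated 138.

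**Step 3: the design at 124.** With 27 failures (97 patent) p = 0.0261, which does not pass. With 26 failures (98 patent) p = 0.0157, which does. Patency power is 83.6%, blood-pressure power 92.6% and joint power 0.836 × 0.926 = 77.4%. The 92% survives; the 27-failure limit, the 87% and the 80% do not.

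**Step 4: how much of the drop is discreteness.**

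| Evaluable n | Failures allowed | Attained alpha | Patency power | Joint power |
|---|---|---|---|---|
| 121 | 26 | 0.0234 | 86.7% | 79.8% |
| 122 | 26 | 0.0205 | 85.7% | 79.0% |
| 123 | 26 | 0.0180 | 84.7% | 78.3% |
| 124 | 26 | 0.0157 | 83.6% | 77.4% |
| 125 | 27 | 0.0230 | 87.6% | 81.3% |
| 126 | 27 | 0.0202 | 86.7% | 80.6% |
| 127 | 27 | 0.0177 | 85.8% | 79.9% |
| 128 | 27 | 0.0155 | 84.8% | 79.1% |

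Power falls while the failure limit is constant and jumps when the limit rises. The plan's 125 sits just after a jump and 124 just before it.

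**Step 5: average over random attrition.** Let the evaluable number be Binomial(N, 0.90) and weight the power at each n by its probability.
- N = 138: patency 85.6%, joint 79.3%.
- N = 139: patency 85.8%, joint 79.6%.

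For 138 enrolled the average shortfalls are 87 − 85.6 = 1.4 points and 80 − 79.3 = 0.7 points.

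**Step 6: the unit.** Protocol 2.1 and SAP 8.8 make patency per lesion, and Protocol 2.1 cites 1.2 lesions per patient. 124 × 1.2 = 148.8, about 149 lesions. The exact test then allows 33 failures with about 92% power if lesions are independent, and less with within-subject correlation.

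**The case against.** A reader might infer that the design misses its stated power by 3.4 points for patency (87 − 83.6) and 2.6 points jointly (80 − 77.4). The documents do not support that. Protocol 5.2 ties the pass mark explicitly to 125 evaluable, and at 125 every figure is right. Ten per cent is a planning allowance, not a fixed outcome: 138 enrolled yields 125 if 13 are lost, which is 13/138 = 9.4%. The value at 124 is also the lowest in its neighbourhood; by the same reasoning, losing three more subjects would raise power from 83.6% to 86.7%. And the loss exists only when subjects are counted, whereas the planned patency analysis counts lesions.

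Nor should anyone conclude that 139 would have restored the stated power. On average it adds about 0.2 points for patency and 0.4 points jointly (before rounding).

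Finally, SAP 6.1 reports that enrolment stopped at 68, and SAP sections 2 and 6.2 make all inference descriptive, so the 26-or-27 boundary will not be applied.

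All of this stands, and it settles the weight of the point. It does not remove the slip. At the plan's own 10%, 138 does not give 125; the Protocol Summary attaches the powers to 138; and SAP 5.5, written after enrolment ended, still carries the uncorrected step.

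**Conclusion.** The slip is real but minor. The enrolment that matches 125 evaluable at 10% attrition is 139, and 138 corresponds to 124. The stated limit and powers are correct at 125. At 124 the limit is 26 failures, with 83.6% patency power and 77.4% joint power. The fairer summary of what 138 supports is about 85.6% and 79.3%, slightly below the stated 87% and 80%.

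These figures rest on the plan's assumed rates and SD, independent endpoints and subjects as the unit; the averages also assume that each subject is lost independently with probability 0.10. The point has no bearing on the descriptive analysis of the 68 enrolled subjects.

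**What to change.** Correct SAP 5.5 and Protocol 5.2, and align the Protocol Summary, in one of two ways.

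1. State that 125 evaluable at 10% attrition corresponds to 139 enrolled, and leave the limit and powers attached to 125 evaluable.
2. Keep 138; state 124 expected evaluable with at most 26 failures; say that the 87% and 80% apply only at 125 evaluable; and give the values at 124 (83.6% and 77.4%) beside the attrition-averaged values (about 85.6% and 79.3%).

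Under either, add a sentence that these calculations are per subject while patency is analysed per lesion.

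The cost is wording. Under the second option the stated power reads slightly less favourably. No further enrolment and no change to the analysis is involved.
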